1. TRIAL OBJECTIVES AND ENDPOINTS

1.1. Primary and Secondary Trial Objectives and Endpoints

The primary and secondary trial objectives and endpoints are as follows:

Objectives	Endpoints
The primary objective of the trial is to evaluate the efficacy of test investigational medicinal product (IMP) as compared to placebo IMP for the preventive treatment of chronic migraine (CM).	The primary efficacy endpoint is the mean change from baseline (28-day baseline period) in the monthly average number of migraine days during the 12-week period after the first dose of IMP.
A secondary objective is to evaluate the safety and tolerability of test IMP in the preventive treatment of CM.	
The safety and tolerability endpoints are as follows:
 
 occurrence of adverse events throughout the trial, including local injection site reaction/pain abnormal standard 12-lead electrocardiogram (ECG) findings changes from baseline in vital signs (systolic and diastolic blood pressure, pulse, temperature, and respiratory rate), height, and weight measurements changes from baseline in clinical laboratory (serum chemistry, hematology, coagulation, and urinalysis) test results abnormal physical examination findings suicidal ideation and behavior as suggested by the Columbia-Suicide Severity Rating Scale (C-SSRS)
A secondary objective of the trial is to further demonstrate the efficacy of test IMP as compared to placebo IMP for the preventive treatment of CM.	
The secondary efficacy endpoints are as follows:
 
 mean change from baseline (28-day baseline period) in monthly average number of headache days of at least moderate severity during the 12-week period after the first dose of IMP proportion of participants reaching at least 50% reduction in the monthly average number of migraine days during the 12-week period after the first dose of IMP mean change from baseline (28-day baseline period) in the monthly average number of days of use of any acute headache medications during the 12-week period after the first dose of IMP mean change from baseline (day 1) in migraine-related disability score, as measured by the Pediatric Migraine Disability Assessment (PedMIDAS) questionnaire, at 12 weeks after administration of the first dose of IMP mean change from baseline (day 1) in quality of life, as measured by the Pediatric Quality of Life Inventory (PedsQL), at 12 weeks after administration of the first dose of IMP

Objectives	Endpoints
A secondary objective of the trial is to evaluate the immunogenicity of test IMP and the impact of antidrug antibodies (ADAs) on clinical outcomes in participants exposed to test IMP	
proportion of participants developing ADAs throughout the trial. The impact of ADAs on safety and efficacy will be analyzed if the number of ADA-positive participants allows.

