### 3. TRIAL OBJECTIVES, ENDPOINTS, AND ESTIMANDS

#### 3.1. Primary and Secondary Trial Objectives and Endpoints

The primary and secondary trial objectives and endpoints are as follows:

Objectives	Endpoints
The primary objective of the trial is to evaluate the efficacy of test investigational medicinal product (IMP) as compared to placebo IMP for the preventive treatment of chronic migraine (CM).	The primary efficacy endpoint is the mean change from baseline (28-day baseline period) in the monthly average number of migraine days during the 12-week period after the first dose of IMP.
A secondary objective is to evaluate the safety and tolerability of test IMP in the preventive treatment of CM.	
The safety and tolerability endpoints are as follows:
 
 
• occurrence of adverse events throughout the trial, including local injection site reaction/pain
 
• abnormal standard 12-lead electrocardiogram (ECG) findings
 
• changes from baseline in vital signs (systolic and diastolic blood pressure, pulse, temperature, and respiratory rate), height, and weight measurements
 
• changes from baseline in clinical laboratory (serum chemistry, hematology, coagulation, and urinalysis) test results
 
• abnormal physical examination findings
 
• suicidal ideation and behavior as suggested by the Columbia-Suicide Severity Rating Scale (C-SSRS)
 

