2. TRIAL DESIGN

2.1. General Design

This is a 4-month, multicenter, randomized, double-blind, placebo-controlled, parallel-group trial to evaluate the efficacy, safety, and tolerability of 2 different doses (dependent on participants' body weight) of subcutaneous (sc) test IMP and placebo IMP. Enrollment will include male and female participants with migraine (6 to 17 years of age, inclusive).

The total duration of the trial is planned to be 75 months (from quarter [Q]2 2020 to Q3 2026).

Participants will be randomly assigned in a 1:1 ratio between test IMP and placebo IMP treatment groups:

- monthly sc administration of test IMP
- monthly sc administration of matching placebo IMP

The dose of test IMP to be administered will be determined by the participant's weight at randomization (visit 2):

- Participants weighing ≥ 45.0 kg will receive monthly sc administration of test IMP at 225 mg.
- Participants weighing <45.0 kg will receive monthly sc administration of test IMP at 120 mg.

The enrollment target is approximately 278 randomized participants in total.

The trial consists of a screening visit, a 28-day baseline period, and a 12-week (84-day) treatment period, including a final evaluation at week 12 (end-of-treatment [EOT] visit, approximately 4 weeks [28 days] after the final dose of IMP).

Blinded treatment will be administered sc once monthly (approximately every 28 days) for a total of 3 doses. Randomization and 1st treatment administration will occur at visit 2 (day 1), and additional doses will be administered at visits 3 and 4 (approximately every 28 days) until the 3rd dose is completed. Final trial assessments will be performed at visit 5 (EOT visit), approximately 28 days after the 3rd (last) dose of IMP. Overall, participants will participate in the current trial for up to 4 months (including a 28-day baseline period and a 12-week, double-blind treatment period).

Participants will be allowed to use acute medications to treat acute migraine attacks, as needed, with the exception of medications containing opioids and barbiturates.

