8. SAFETY ANALYSIS

8.1. General

The safety population will be used for all safety analyses. Summaries will be presented by treatment group (TEV-48125 225 mg, TEV-48125 120 mg and placebo). TEV-48125 will be presented as actually received unless specified otherwise. A total column will also be provided.

For continuous variables, descriptive statistics (n, mean, SD, median, minimum, and maximum) will be provided for actual values and changes from baseline to each time point. For categorical variables, participant counts and percentages will be provided.

Missing values will be reported as missing and no imputation will be undertaken.

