8.7. Physical Examinations

Physical examinations, including height and weight (to be obtained at the screening visit, randomization visit, and EOT only) and puberty status (at randomization and EOT only) will be performed at the selected time points during the trial. Body mass index will be calculated at screening and randomization.

A complete physical examination will include the following organ systems: general appearance; head, eyes, ears, nose, and throat; chest and lungs; heart; abdomen; musculoskeletal; skin; lymph nodes; and neurological. Any physical examination finding that is judged by the Investigator as a potentially clinically significant change (worsening) compared with a baseline value will be considered an adverse event and recorded on the CRF.

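### Raw height and weight changes at 120 mg (all under 45.0 kg) are set against a placebo column of all weights, so a growth difference could be masked or mimicked

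*SAP*

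**What the plan says.** SAP 1.1 names this among the safety endpoints: "changes from baseline in vital signs (systolic and diastolic blood pressure, pulse, temperature, and respiratory rate), height, and weight measurements". Protocol 3.1 has the same item.

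SAP 8.7 gives only the timing: "Physical examinations, including height and weight (to be obtained at the screening visit, randomization visit, and EOT only"). It adds puberty status at randomization and EOT and states no summary for any of these. SAP 8.8 and its Table 5 deal with pulse, blood pressure, respiratory rate and temperature. SAP 5.7 lists physical examination results and summarises abnormal findings. Protocol 9.5 names laboratory, ECG and vital signs data.

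That leaves the general rule in SAP 8.1. Its rule for data on a continuous scale is that "descriptive statistics (n, mean, SD, median, minimum, and maximum) will be provided for actual values and changes from baseline to each time point". On layout it says: "Summaries will be presented by treatment group (TEV-48125 225 mg, TEV-48125 120 mg and placebo"), plus a total column. SAP 2.1 fixes who can be in each active column: "The dose of test IMP to be administered will be determined by the participant's weight at randomization (visit 2"), with 120 mg below 45.0 kg and 225 mg at or above it.

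The split into ages 6–11 and 12–17 is stated for the adverse event tables only (SAP 8.4). Neither document mentions a z-score or growth-reference adjustment for the height and weight endpoint.

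**The concern.** Participants are 6 to 17 years old, and over 12 weeks a younger, lighter child can be expected to gain more height than an older, heavier one. The 120 mg column contains only the lighter children. The placebo column mixes light and heavy children. The two would therefore differ on raw height change even if the drug did nothing.

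A reader scanning the table could be misled in either direction. A real slowing at 120 mg could be cancelled by the faster natural growth of that column. Conversely, ordinary growth could look like a drug effect: faster growth at 120 mg, or slower growth at 225 mg. What is at stake is the readability of a stated pediatric safety endpoint, not the efficacy result.

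**Working it through.** The documents give no figure for height or weight, so there is nothing of the plan's own to reproduce.

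**Inputs from the documents**
- Treatment period: 12 weeks (SAP 2.1).
- Columns: 225 mg, 120 mg, placebo (SAP 8.1).
- Dose cut at 45.0 kg at randomization (SAP 2.1).
- Allocation 1:1, stratified by country, sex, puberty status and preventive use, not by weight or age (SAP 2.2).
- 139 randomized per arm (SAP 2.4).

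**Assumptions, not in the documents**
- Height growth of 5–6 cm/year below 45.0 kg and 1–2 cm/year at or above it.
- Share below 45.0 kg, p: 15–35%.

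**Formulas under no drug effect.** Let L and H be the expected 12-week changes in the light and heavy strata, with G = L − H. The placebo column has expected change pL + (1−p)H. Then:
- 120 mg minus placebo = L − pL − (1−p)H = (1−p)G
- 225 mg minus placebo = H − pL − (1−p)H = −pG
- all active minus placebo = p(1−p)G − (1−p)pG = 0

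**Numbers.** Twelve weeks is 12/52 = 0.231 year. So L = 1.15–1.38 cm and H = 0.23–0.46 cm.

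| Growth, light / heavy (cm/year) | G (cm) | 120 mg − placebo, p = 15% | 120 mg − placebo, p = 35% | 225 mg − placebo, p = 15% | 225 mg − placebo, p = 35% |
|---|---|---|---|---|---|
| 5 / 1 | 0.92 | 0.78 | 0.60 | −0.14 | −0.32 |
| 5 / 2 | 0.69 | 0.59 | 0.45 | −0.10 | −0.24 |
| 6 / 1 | 1.15 | 0.98 | 0.75 | −0.17 | −0.40 |
| 6 / 2 | 0.92 | 0.78 | 0.60 | −0.14 | −0.32 |

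The built-in difference at 120 mg is thus 0.45 to 0.98 cm. A true slowing of exactly (1−p)G would bring it to zero.

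**Smaller gaps.** With G of 0.25 to 1.0 cm and p of 15–40%, the difference is 0.15 cm (0.60 × 0.25) to 0.85 cm (0.85 × 1.0). The size depends on the assumptions. The sign does not, as long as lighter children grow faster.

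**All active versus all placebo.** The expected difference is 0. Chance imbalance in the light share adds an SD of G√(2p(1−p)/139). This is 0.69 × 0.043 = 0.03 cm at the low end and 1.15 × 0.057 = 0.07 cm at the high end.

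**Placebo within the same weight stratum.** The expected difference is L − L = 0 or H − H = 0, already on the raw scale.

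The same formulas apply to weight in kilograms. No growth figures were assumed for weight, so no size is given for it.

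**The case against.** The strongest reply is that the plan does what it says. The endpoint is a change from baseline, SAP 8.1 reports changes from baseline, and no growth-velocity question is posed. The documents name no growth risk, the table is descriptive with no test, and a physical examination finding judged a potentially clinically significant worsening becomes an adverse event, tabulated by age group. All of that stands and keeps the point small. It does not remove the column mismatch: individual adverse event judgements do not make up for a mean comparison between unlike groups.

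The second reply is that randomization protects the comparison. This also stands, for the contrast it covers. A reader might infer that raw change biases active against placebo. It does not: allocation is 1:1 and stratified by sex and puberty status, and the expected all-active difference is zero. There the raw scale only adds age-related spread. The risk of masking or mimicking comes mainly from the column layout.

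A reader might also infer that halved growth at 120 mg would go unnoticed. That does not hold across the assumed range. The built-in difference is (1−p)(1 − H/L) of the light children's expected growth. This runs from 39% (5/2 cm/year, p = 35%) to 71% (6/1 cm/year, p = 15%). At p = 35%, halved growth would fall below the placebo mean in two cases: 0.58 against 0.70 cm (5/2) and 0.69 against 0.78 cm (6/2).

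On the remedy, it is fair to say that 12 weeks is short for z-score change and that the eligibility criterion on BMI percentile uses the local standard, not a common reference.

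**Conclusion.** The point holds as a modest one. Height and weight change is a named safety endpoint, and the only rule that reaches it sets a weight-selected 120 mg column against an unselected placebo column. With no drug effect, the expected height difference at 120 mg is (1−p)G, or 0.45–0.98 cm over 12 weeks under the assumed growth rates and p of 15–35%. That could mask or mimic a growth difference at 120 mg; the opposite artefact at 225 mg is 0.10–0.40 cm. The growth rates and p are assumptions. The column structure is in the documents.

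A reader might conclude that the endpoint is uninformative or that the drug is suspected of affecting growth. The documents support neither. The all-active comparison is unbiased and can be recovered by weighting the two dose columns by their numbers, although the SAP does not say it will be shown. Efficacy conclusions are untouched.

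**What to change.** In SAP 8.7, add a height and weight summary with these parts:
- Change from randomization (visit 2) to EOT in age- and sex-standardised height and weight z-scores, and in BMI z-scores derived from them. Use one named growth reference and age at each measurement.
- Raw values and raw changes alongside.
- Placebo shown separately below 45.0 kg and at or above 45.0 kg, next to the matching dose column, plus all active against all placebo.

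The weight-matched placebo columns remove the expected artefact. The z-scores reduce the remaining spread from age and sex.

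The cost is SAP wording and one derived table. Height and weight are already taken at randomization and EOT, and sex and date or year of birth are collected (SAP 5.3). No new assessment or change in sample size is needed. The downsides are that one reference must serve all countries, 12 weeks is short for z-score change, EOT BMI must be derived because it is planned only at screening and randomization, and z-scores will be less exact for any participant with only a year of birth.

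The note to file dated 29 May 2025 says the trial analysis has been conducted. If the SAP can no longer be amended, SAP 2.5.2 allows additional exploratory analyses to be reported in appendices to the CSR, and the table can go there.

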1.2. Exploratory Objective and Endpoints

Term	Percentage
GMOs	85%
Organic	80%
Natural	75%
Artificial	45%
Organic	85%
Natural	80%
Artificial	45%
Organic	85%
Natural	80%
Artificial	45%

2. TRIAL DESIGN

2.1. General Design

This is a 4-month, multicenter, randomized, double-blind, placebo-controlled, parallel-group trial to evaluate the efficacy, safety, and tolerability of 2 different doses (dependent on participants' body weight) of subcutaneous (sc) test IMP and placebo IMP. Enrollment will include male and female participants with migraine (6 to 17 years of age, inclusive).

The total duration of the trial is planned to be 75 months (from quarter [Q]2 2020 to Q3 2026).

Participants will be randomly assigned in a 1:1 ratio between test IMP and placebo IMP treatment groups:

- monthly sc administration of test IMP
- monthly sc administration of matching placebo IMP

The dose of test IMP to be administered will be determined by the participant's weight at randomization (visit 2):

- Participants weighing ≥ 45.0 kg will receive monthly sc administration of test IMP at 225 mg.
- Participants weighing <45.0 kg will receive monthly sc administration of test IMP at 120 mg.

The enrollment target is approximately 278 randomized participants in total.

The trial consists of a screening visit, a 28-day baseline period, and a 12-week (84-day) treatment period, including a final evaluation at week 12 (end-of-treatment [EOT] visit, approximately 4 weeks [28 days] after the final dose of IMP).

Blinded treatment will be administered sc once monthly (approximately every 28 days) for a total of 3 doses. Randomization and 1st treatment administration will occur at visit 2 (day 1), and additional doses will be administered at visits 3 and 4 (approximately every 28 days) until the 3rd dose is completed. Final trial assessments will be performed at visit 5 (EOT visit), approximately 28 days after the 3rd (last) dose of IMP. Overall, participants will participate in the current trial for up to 4 months (including a 28-day baseline period and a 12-week, double-blind treatment period).

Participants will be allowed to use acute medications to treat acute migraine attacks, as needed, with the exception of medications containing opioids and barbiturates.

Upon completion of the final trial assessments, all eligible participants will be offered enrollment in a long-term safety and tolerability trial (Trial TV48125-CNS-30084), consisting of 9 months (36 weeks) of open-label treatment and 5 months of follow-up commencing from the last IMP administration. In the long-term safety extension trial, participants rolling over from the current trial will be weighed at visit 2 and will receive monthly test IMP with dose adjusted per weight category (225 mg in participants ≥ 45.0 kg or 120 mg in participants <45.0 kg). Participants who do not complete this trial and participants who complete this trial but do not wish to continue treatment may enroll in Trial TV48125-CNS-30084 for the purpose of attending a follow-up visit

for safety and ADA assessments approximately 5 months (150 days [5 half-lives]) after receiving the last dose of IMP.

Trial procedures and assessments with their time points are shown in the protocol. The trial schematic diagram is shown in [Figure 1](#).

The end of trial is defined as the date the last participant attends the EOT/early withdrawal visit (visit 5).

Figure 1: Overall Trial Schematic Diagram

Patients weighing ≥ 45.0 kg at randomization:

[figure not shown]
[figure not shown]

Figure 1: Overall Trial Schematic Diagram (Continued)

Patients weighing <45.0 kg at randomization:

PBO=placebo; SC=subcutaneous; V=visit.

2.2. Randomization and Blinding

This is a double-blind trial. The Sponsor, Investigators, trial staff (except for staff involved in bioanalytical analyses), and participants will be blinded to treatment assignment. A computer-generated master randomization list will be provided to drug packaging facilities. Packaging vendor(s) will package active and placebo into single-visit kits according to Good Manufacturing Practice procedures. The active drug and placebo kits for each dose will be identical in appearance and will contain 1 pre-filled syringe (PFS) (for the 225 mg dose and its matching placebo) or 2 vials (for the 120 mg dose and its matching placebo). Adequate kit supply for upcoming trial visits will be managed by interactive response technology (IRT) and kept (refrigerated at 2°C to 8°C) on site.

This is a randomized trial. Randomization will be stratified by country, sex, puberty status, and preventive medication use at baseline (Yes/No). Participants will be randomly assigned to treatment groups by means of a computer-generated randomization list. The specifications for randomization will be under the responsibility and oversight of Teva Global Statistics. Each participant will undergo randomization in a 1:1 ratio within the stratum to which he or she belongs to receive test IMP or placebo IMP, as assigned by the IRT. The IRT will manage initial drug supply, maintenance of adequate IMP supplies on site, and trial randomization centrally. At the time of each trial visit, the IRT will be queried, and site personnel will retrieve and administer a 1.5 mL volume for participants weighing ≥ 45.0 kg at randomization (visit 2) or a 0.8 mL volume for participants weighing <45.0 kg at randomization (visit 2) from each PFS or 2 vials contained in the appropriately numbered kit(s).

The Sponsor's clinical personnel (and delegates) involved in the trial will be blinded to the identity of the IMPs until the database is locked for analysis and the IMP assignment is known. However, if a prioritized sample analysis is needed, bioanalytical and clinical pharmacology personnel may be unblinded.

In the event of an emergency, it will be possible to determine to which treatment group and dose the participant has been allocated by accessing the Randomization and Trial Supply Management (RTSM) system. All investigational centers will be provided with details of how to access the system for code breaking at the start of the trial. The Medical Monitor or equivalent should be notified following unblinding. Any unblinding of the IMP performed by the Investigator must be recorded in the source documents.

2.3. Data Monitoring Committee

There will be no Data Monitoring Committee in this trial.

2.4. Sample Size and Power Considerations

The sample size planned is approximately 266 participants (133 evaluable participants completing the trial per treatment group). Assuming a treatment difference of 1.7 days (reduction in monthly average number of headache days of at least moderate severity) and a common SD of 4.92, a sample size of 133 participants per treatment group gives at least 80% power for the trial to succeed at an alpha level of 0.05. Assuming a 4% discontinuation rate, approximately 278 participants (139 participants per treatment group) will be randomized. Participants will be randomized to receive either monthly sc administration of test IMP or placebo IMP.

The enrollment target is approximately 278 participants in total.

2.5. Sequence of Planned Analyses

2.5.1. Planned Interim Analyses

There will be no interim analysis in this trial.

2.5.2. Final Analyses and Reporting

All analyses identified in this SAP will be performed after the end of trial as defined in the trial protocol. This SAP and any corresponding amendments will be approved before database lock and subsequent unblinding, in accordance with GSD-SOP-702 (Statistical Analysis Plan).

Any exploratory analyses completed to support trial analyses, which are not identified in this SAP, will be documented and reported in appendices to the CSR.

